#### Diarrhea

Diarrhea should be treated promptly with appropriate supportive care, including loperamide. Subjects should be instructed to begin taking loperamide at the first sign of: 1) poorly formed or loose stool, 2) occurrence of more bowel movements than usual in 1 day, or 3) unusually high volume of stool. Loperamide should be taken in the following manner: 4 mg at first onset of diarrhea, then 2 mg after each unformed stool. The daily dose of loperamide should not exceed 16 mg/day. Loperamide should be deferred if blood or mucus is present in the stool or if diarrhea is accompanied by fever. In this setting, appropriate diagnostic microbiologic specimens should be obtained to exclude an infectious etiology. Subjects should be also advised to drink liberal quantities of clear fluids to help prevent dehydration. Supportive care with steroids (as described in Section 6.5.3.2).

## Skin Toxicity

Clinical judgment and experience of the treating physician should guide the management plan of each participant. In general, the following interventions are in addition to the rash dosing adjustment guidelines in [Table 5](#) Dose Modification and Toxicity Management Guidelines for Immune-related Adverse Events Associated with Pembrolizumab Monotherapy, Coformulations or IO Combinations:

- Prophylaxis of skin toxicity to be initiated 24 hours prior to the first treatment with study drug or later as needed.
- Application of topical agents to the most commonly affected skin areas such as face, scalp, neck, upper chest and upper back.

Topical agents include non-oily sunscreen (para-aminobenzoic acid free, SPF  $\geq 30$ , ultraviolet A/ultraviolet B protection), topical steroids (preferably mometasone cream, ie, Elocon®) and topical erythromycin (ie, Eryaknen® or topical pimecrolimus).

**Note:** Topical agents should be applied on a daily basis starting on Day 1 of study treatment or 24 hours prior to the first dose, and more often as needed.

- Possibly oral doxycycline (100 mg daily) for the first 2 to 3 weeks of study drug administration.

Other effective medications are antihistamines, other topical corticosteroids, other topical antibiotics and low-dose systemic corticosteroids.

The treatment algorithm based on CTCAE grade is as follows:

### Mild rash (CTCAE Grade 1)

- Consider prophylactic rash treatment if not already started.
- Topical or other topical corticosteroid (ie, mometasone cream) and/or topical antibiotic (ie, erythromycin 2%) are recommended.
- The participant should be reassessed by the investigator.

### Moderate rash (CTCAE Grade 2)

- Use of topical erythromycin or clindamycin (1%) plus topical mometasone or pimecrolimus cream (1%) plus oral antibiotics such as: lymecycline (408 mg once daily), doxycycline (100 mg BID) or minocycline (50 to 100 mg once daily).
- Although there has been no evidence of phototoxicity or photosensitivity in participants being treated with selumetinib, doxycycline (or minocycline as second-line) should be

used with thorough ultraviolet protection (ie, avoidance of direct exposure to sunlight, use of sunscreen and sunglasses).

- Use of acitretin is not recommended.

### **Severe rash (CTCAE Grade 3 to 4)**

#### **CTCAE Grade 3**

- In addition to the interventions recommended for moderate rash, consider oral prednisolone at a dose of 0.5 mg/kg. Upon improvement, taper the dose in a stepwise manner (25 mg for 7 days, subsequently decreasing the dose by 5 mg/day every day).
- Alternatively, in addition to the interventions recommended for moderate rash, consider oral isotretinoin (low doses, ie, 0.3 to 0.5 mg/kg) [Lacouture, M. E., et al 2011].
- Use of acitretin is not recommended.

#### **CTCAE Grade 4**

- Immediately discontinue the participant from study drug and treat the participant with oral and topical medications (see recommendation CTCAE Grade 3).

#### **Symptomatic Treatment:**

It is strongly recommended that participants who develop rash/skin toxicities receive symptomatic treatment:

- For pruritic lesions, use cool compresses and oral antihistaminic agents
- For fissuring, use Monsel's solution, silver nitrate, or zinc oxide cream. If not sufficient use mild steroid ointments or combinations of steroids and antibiotics such as Fucicort®
- For desquamation, use emollients with mild pH 5/neutral (best containing urea 10%)
- For paronychia, antiseptic bath and local potent corticosteroids, use oral antibiotics and if no improvement is seen, refer to a dermatologist or surgeon
- For infected lesions, obtain bacterial and fungal cultures and treat with topical or systemic antibiotics based on sensitivity of culture

#### **6.5.3.2 Pembrolizumab Supportive Care Guidelines**

Subjects should receive appropriate supportive care measures as deemed necessary by the treating investigator. Suggested supportive care measures for the management of AEs with potential immunologic etiology are outlined along with the dose modification guidelines in Section 6.6.1.2, [Table 6](#). Where appropriate, these guidelines include the use of oral or IV treatment with corticosteroids, as well as additional anti-inflammatory agents if symptoms do

not improve with administration of corticosteroids. Note that several courses of steroid tapering may be necessary as symptoms may worsen when the steroid dose is decreased. For each disorder, attempts should be made to rule out other causes such as metastatic disease or bacterial or viral infection, which might require additional supportive care. The treatment guidelines are intended to be applied when the Investigator determines the events to be related to pembrolizumab.

Note: If after the evaluation of the event, it is determined not to be related to pembrolizumab, the investigator does not need to follow the treatment guidance. Refer to Section 6.6.1.2, [Table 6](#) for guidelines regarding dose modification and supportive care.

## **6.6 Dose Modification (Escalation/Titration/Other)**

### **6.6.1 Dose Modifications Due to Adverse Events**

In previous studies of selumetinib and pembrolizumab monotherapy, overlapping toxicities have been observed for selumetinib and pembrolizumab (refer to IBs). These overlapping toxicities include pneumonitis, diarrhea/colitis, cardiac function decrease, and skin rash.

In the current study, the relationship of these AEs to selumetinib and/or pembrolizumab may be difficult to unambiguously assign. Therefore, if a participant experiences an AE related to either treatment, both selumetinib and pembrolizumab will be modified or discontinued as described in [Table 4](#) and [Table 5](#).

If 2 different therapies are proposed in these tables, the most conservative/effective treatment should be chosen (ie, steroid). Further, if the investigator believes the treatment emergent toxicity is unambiguously related to only one of the agents, they may continue the participant on the unrelated agent following consultation with the Sponsor.

#### **6.6.1.1 Selumetinib Dose Modification Due to Adverse Events**

The starting dose level for selumetinib is 50 mg BID, and a dose reduction below 50 mg BID is not allowed. Participants requiring additional reductions must discontinue selumetinib treatment.

Missed/skipped doses will not be made up (ie, the participant should not double their dose if the previous dose was missed). When a toxicity results in a dose reduction, the dose cannot be re-escalated.

Dose reduction/interruption/discontinuation decisions should be based on the CTCAE grade of the toxicity and the guidelines provided below. In general, doses should not be reduced or interrupted for Grade 1 toxicities, but treatment to control symptoms should be provided as appropriate.

[Table 4](#) provides dose adjustment recommendations for selumetinib-induced toxicities. During dose interruption the site should consult with the Sponsor regarding the discontinuation and/ or resumption of treatment.

Table 4 Dose Modification Guideline for Selumetinib

Eye disorders- Retinal Events (including serious detachment of the retina)	
Grade 1	Maintain dose level of selumetinib and repeat ophthalmic monitoring including visual acuity assessment and OCT within 10 days.
Grade 2	
Interrupt selumetinib dosing and refer the participant to ophthalmologist within 1 week and obtain OCT within 10 days:
 

• If resolved to baseline or Grade <math>\leq 1</math> within 10 days, resume treatment at current dose level; continue the schedule of visual assessments established per protocol.

• If not resolved to baseline or Grade <math>\leq 1</math> within 10 days, resume treatment at 1 reduced dose level (1 level below that previously received); continue the schedule of visual assessments established per protocol.

• If on retreatment Grade 2 reoccurs, permanently discontinue selumetinib.

Grade 3	
Interrupt selumetinib and refer the participant to ophthalmologist within 1 week and obtain OCT:
 

• If resolved to baseline or Grade <math>\leq 1</math> within 7 days, resume treatment at current dose level; continue the schedule of visual assessments schedule established per protocol.

• If not resolved to baseline or Grade <math>\leq 1</math> within 7 days, continue to hold the selumetinib dose and repeat ophthalmic assessment in 10 days.

• If resolved to baseline or Grade <math>\leq 1</math>, resume treatment at 1 reduced dose level; continue the schedule of visual assessments established per protocol.

• If remains Grade 3, permanently discontinue selumetinib.

• If on retreatment Grade 3 reoccurs, permanently discontinue selumetinib.

Grade 4	Permanently discontinue selumetinib and immediately follow up with ophthalmic monitoring.

Eye disorder - RVO	
Any Grade	Permanently discontinue selumetinib.
Other eye disorders (ie, Non-retinal Events)	
Grade 1 to -2	Maintain dose level of selumetinib and increase frequency of ophthalmic monitoring to at least 14 days until stabilization or resolution.
Grade 3	
Interrupt selumetinib and refer participant to ophthalmologist within 1 week:
 
 
• If resolved to Grade <math>\leq 1</math> in <math>\leq 21</math> days, resume treatment at 1 reduced dose level.
 
• If not resolved to Grade <math>\leq 1</math> in <math>\leq 21</math> days, permanently discontinue selumetinib.
 

Grade 4	Permanently discontinue selumetinib.
Liver-related adverse events	
Grade 1 AST or ALT ( $>\text{ULN}$ to $3 \times \text{ULN}$ )	Maintain dose level of selumetinib.
Grade 2 AST or ALT ( $>3$ to $5.0 \times \text{ULN}$ ) or $3 \times$ baseline value (if liver metastasis) AND blood bilirubin $\leq 2.0 \times \text{ULN}$	
Interrupt dose of selumetinib until resolved to Grade <math>\leq 1</math> (or Grade <math>\leq 2</math> in case of liver metastasis), then:
 
 
• If resolved in <math>\leq 14</math> days, resume treatment at current dose level and schedule.
 
• If resolved in <math>>14</math> days, resume treatment at 1 reduced dose level.
 
 
Recurrence:
 
 
• Interrupt dosing of selumetinib until resolved to Grade <math>\leq 1</math> (or Grade <math>\leq 2</math> in case of liver metastasis), then resume treatment at 1 reduced dose level.
 

Grade 2 AST or ALT ( $>3$ to $5.0 \times \text{ULN}$ or $3 \times$ baseline value (if liver metastasis) AND blood bilirubin $>2.0 \times \text{ULN}$	
Interrupt dose of selumetinib until resolved to Grade <math>\leq 1</math> (or Grade <math>\leq 2</math> in case of liver metastasis), then:
 
 
• If resolved in <math>\leq 7</math> days, resume treatment at 1 reduced dose level. If not resolved in <math>\leq 7</math> days, permanently discontinue selumetinib.
 

Grade 3 AST or ALT ( $>5.0$ to $8.0 \times$ ULN) AND blood bilirubin $\leq 2.0 \times$ ULN	Interrupt dose of selumetinib until resolved to Grade $\leq 1$ (or Grade $\leq 2$ in case of liver metastasis), then: 
 
• If resolved in <math>\leq 14</math> days, resume treatment at current dose level and schedule.
 
• If resolved in <math>>14</math> days, resume treatment at 1 reduced dose level.
 
 Recurrence: 
 
• Interrupt dosing of selumetinib until resolved to Grade <math>\leq 1</math> (or Grade <math>\leq 2</math> in case of liver metastasis), then resume treatment at 1 reduced dose level.
 

AST or ALT ( $>8 \times$ ULN) AND blood bilirubin* $\leq 2.0 \times$ ULN	Permanently discontinue selumetinib.
AST or ALT ( $>5.0 \times$ ULN) AND blood bilirubin* $>2.0 \times$ ULN	Permanently discontinue selumetinib.
AST or ALT Grade 4 ( $>20.0 \times$ ULN)	Permanently discontinue selumetinib.
Cardiac disorders	
Left ventricular systolic dysfunction Asymptomatic decrease of $>10\%$ in LVEF compared to baseline and the LVEF is below the institution's lower limit of normal	Interrupt dose of selumetinib and repeat evaluation of LVEF within 2 weeks. 
 
• If the LVEF recovers (defined as LVEF <math>\geq 50\%</math> or <math>\geq</math> LLN and absolute decrease <math>\leq 10\%</math> compared to baseline) <math>\leq 3</math> weeks, resume treatment at 1 reduced dose level after approval by the Sponsor Medical Monitor. Monitor LVEF 2 weeks after restarting on selumetinib, every 4 weeks for 12 weeks and subsequently as per protocol.
 
• If the LVEF does not recover within 3 weeks, permanently discontinue participant from study treatment. Closely monitor LVEF until resolution (or 16 weeks).
 

Grade 3 to 4	Permanently discontinue participant from selumetinib. Closely monitor LVEF until resolution (or 16 weeks).
CK elevation	
Grade 1 to 2	Continue treatment on same dose level. Ensure patient is adequately hydrated. Monitor closely CK and serum creatinine levels. (If total CK $\geq 3 \times$ ULN, measure isoenzymes and myoglobin in blood and urine).

Grade 3 (>5.0 to 10.0 x ULN) without renal impairment (ie, serum creatinine <1.5 x ULN or 1.5 x baseline)	If asymptomatic, maintain dose of selumetinib. Monitor closely and measure isoenzymes and myoglobin in blood and urine. If symptomatic (muscle pain/spasms or muscle weakness), interrupt dose of selumetinib until resolved to CTCAE Grade $\leq 1$ and monitor closely, then: 

• If resolved in <math>\leq 21</math> days, then resume treatment at 1 reduced dose level.

• If resolved in <math>>21</math> days, permanently discontinue selumetinib.

Grade 4 (>10 x ULN) without renal impairment (ie, serum creatinine <1.5 x ULN or 1.5 x baseline)	If asymptomatic, interrupt dose of selumetinib and monitor closely. Ensure patient is adequately hydrated and monitor and measure isoenzymes and myoglobin in blood or urine, and serum creatinine. 

• If resolved in <math>\leq 21</math> days, then resume treatment at 1 reduced dose level.

• If resolved in <math>>21</math> days, permanently discontinue selumetinib.

 If symptomatic, permanently discontinue selumetinib. If symptomatic (muscle pain/spasms), permanently discontinue selumetinib.
Grade 3 or 4 with renal impairment (ie, serum creatinine $\geq 1.5$ x ULN or 1.5 x baseline)	Interrupt selumetinib dose until resolved to Grade $< 1$ or baseline level. Ensure patient is adequately hydrated. Monitor isoenzymes and myoglobin in blood or urine, and serum creatinine, then: 

• If resolved in <math>\leq 21</math> days, then resume treatment at 1 reduced dose level.

• If resolved in <math>>21</math> days, permanently discontinue selumetinib.

 Recurrence: 

• Permanently discontinue selumetinib.

Rash	
Grade 1	Treatment with selumetinib will be maintained at the current dose. Initiate prophylactic regimen if it was not already and monitor closely.
Grade 2	First occurrence: 

• Treatment with selumetinib will be maintained at the current dose and rash will be closely monitored. Initiate prophylactic regimen if it was not already started.

• Reassess within a maximum of two weeks. If rash worsens or does not improve, interrupt dosing until improvement to Grade <math>\leq 1</math>. Resume treatment at the current dose level.

 Second occurrence: 

• Reassess within a maximum of 2 weeks. If rash worsens or does not improve, interrupt dosing until improvement to Grade <math>\leq 1</math>. Resume treatment at 1 reduced dose level.

• Only one dose reduction is permitted.

Grade 3	
First occurrence:
 
 
Treatment with selumetinib will be interrupted. Reassess the participant weekly. Consider referral to dermatologist and manage rash per dermatologist's recommendation.
 
Interrupt treatment until improvement to Grade <math>\leq 1</math>. Resume treatment of the current dose level and schedule.
 
 
Second occurrence:
 
 
Interrupt treatment until improvement to Grade <math>\leq 1</math>. Resume treatment with selumetinib at a reduced dose level. If participant is at the lowest dose, participant will be discontinued.
 
Consider referral to dermatologist and manage rash per dermatologist's recommendation.
 

Grade 4	Permanently discontinue selumetinib.
Diarrhea	
Uncomplicated Grade 1 to 2	Consider temporary interruption of selumetinib until resolved to Grade $\leq 1$ . Resume treatment of the current dose level and schedule.
Complicated Grade 1 to 2	Temporarily interrupt selumetinib treatment until resolved to Grade $\leq 1$ . Resume treatment at 1 reduced dose level. If participant is at the lowest dose, participant will be discontinued.
Grade 3 to 4	Temporarily interrupt selumetinib treatment until resolved to Grade $\leq 1$ . Resume treatment at 1 reduced dose level. If participant is at the lowest dose, participant will be discontinued.
Nausea/Vomiting	
Grade 1 to 2	Treatment with selumetinib will be maintained at the current dose. Promptly institute antiemetic measure.
Grade 3	Temporarily interrupt selumetinib treatment until resolved to Grade $\leq 1$ . Resume treatment at the current dose level if, in the judgment of the investigator, the toxicity is considered to be unrelated to selumetinib, or at 1 reduced dose level. Note: Interrupt dose for $\geq$ Grade 3 vomiting or Grade 3 nausea only if the vomiting or nausea cannot be controlled with optimal antiemetics (as per local practice).
Grade 4	Permanently discontinue selumetinib treatment
Interstitial lung disease/pneumonitis	
Grade 1	Maintain dose level of selumetinib. Monitor weekly.
Grade 2	Withhold selumetinib for up to 3 weeks. If improved to Grade 0 or 1, resume treatment at 1 reduced dose level. If not resolved within 3 weeks, permanently discontinue selumetinib.
Grade 3 to 4	Permanently discontinue selumetinib.

Venous Thromboembolism	
Uncomplicated DVT or PE	Withhold selumetinib for up to 3 weeks. If improved to Grade 0 or 1, resume treatment at 1 reduced dose. If not improved, permanently discontinue.
Life threatening PE	Permanently discontinue selumetinib.
All other adverse events (suspected to be related)	
Grade 1 to 2	If the event is a persistent Grade 2 AE not responsive to a specific therapy, consider study drug interruption or reduction.
Grade 3	For other AEs, interrupt study drug until resolution to Grade $\leq 1$ or to pre-treatment/baseline level. If the event resolves within 21 days, then study drug may be resumed at 1 reduced dose level (1 level below that previously received) based upon the investigator's discretion.
Grade 4	Permanently discontinue study drug.

Abbreviations: AE=adverse event; ALT=alanine aminotransferase; AST=aspartate aminotransferase; BID= twice daily; CK=creatine kinase; CTC=Common Terminology Criteria; DVT=deep vein thrombosis; ECG=electrocardiogram; LLN= lower limit of normal; LVEF=left ventricular ejection fraction; OCT= ocular coherence tomography; PE=pulmonary embolism; RVO=retinal vein occlusion; QTc=Q-T interval QTcF=QT interval calculated according to the Fridericia method; ULN= upper limit of normal.

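### Table 4, Grade 2 AST/ALT rows: in liver metastasis, a selumetinib hold started at >3 to 5.0 x ULN begins with its enzyme resume target already met

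*Combined protocol and SAP*

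**What the plan says.** Table 4 has two Grade 2 AST/ALT rows, separated by whether bilirubin is at most 2.0 x ULN or above it. Both are triggered by a value of >3 to 5.0 x ULN, or by three times the "baseline value (if liver metastasis) AND blood bilirubin" condition. Both hold selumetinib until Grade 1 or less, with Grade 2 or less allowed "in case of liver metastasis), then" the timing rules follow:

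- **Bilirubin at most 2.0 x ULN.** Resolved within 14 days: same dose. Resolved later: one level lower. After a recurrence: hold to the same target, then one level lower.
- **Bilirubin above 2.0 x ULN.** Resolved within 7 days: one level lower. Otherwise selumetinib stops permanently.

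The text of Section 6.6.1.1 sets the scale: "Dose reduction/interruption/discontinuation decisions should be based on the CTCAE grade of the toxicity and the guidelines provided below". It defines no baseline-adjusted grade. No reduction below 50 mg BID is allowed: "Participants requiring additional reductions must discontinue selumetinib treatment". On oversight it adds: "During dose interruption the site should consult with the Sponsor regarding the discontinuation and/ or resumption of treatment". Table 2 (Section 5.1) admits participants with liver metastases at AST/ALT up to 5 x ULN.

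**The concern.** A hold is useful only if its release condition lies below its trigger. In these two rows the relaxed liver-metastasis target covers the whole range that the table labels Grade 2, so a participant held at 4 x ULN already qualifies to restart.

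Three things are at stake. First, the rule sets no enzyme recovery threshold in a subgroup for which the protocol writes specific hepatic rules. Second, with bilirubin at most 2 x ULN, the table does not show whether a second reading of 4 x ULN is the same event (same dose) or a recurrence (one level lower, or stop at 50 mg BID). Sites could decide this differently, and study drug discontinuation due to an AE is a primary endpoint (Section 3). Third, with bilirubin above 2 x ULN, the test that decides between restart and permanent discontinuation may have nothing to measure on the enzyme side. Treatment can run to 35 cycles while the DLT window is 21 days, so most exposure to this rule falls outside that window.

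**Working it through.** The plan gives no figure to reproduce; this is a logic check on Table 4's cut-offs. Let x be AST or ALT and b the baseline value, both in multiples of ULN.

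**Inputs.** Table 4: Grade 1 is x >1 to 3, Grade 2 is x >3 to 5, and the Grade 3 row is x >5 to 8. Hence Grade 1 or less means x ≤ 3, and Grade 2 or less means x ≤ 5. Table 2: b ≤ 5 with liver metastases.

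**Step 1. Both triggers apply in liver metastasis (>3 to 5.0 x ULN, or three times baseline).** For a hold started by the ULN range, the trigger is 3 < x ≤ 5 and the target is x ≤ 5. At x = 3.01, 3.5, 4, 4.5 and 5 the liver-metastasis target is met at once. The target without liver metastasis (x ≤ 3) is met at none of them. Time to enzyme resolution is therefore 0 days. The >14-day reduction and the 7-day discontinuation cannot be reached on enzymes unless x rises above 5.

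**Step 2. Three times baseline replaces the ULN trigger.** The target is met at the trigger when 3b ≤ 5, that is b ≤ 5/3 = 1.67.

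| b | 3b | Target (≤ 5) already met? |
|---|---|---|
| 1.2 | 3.6 | yes |
| 1.5 | 4.5 | yes |
| 1.67 | 5.0 | yes |
| 2 | 6 | no |
| 3 | 9 | no |
| 5 | 15 | no |

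**Step 3. The Grade 3 row, for contrast.** The trigger is 5 < x ≤ 8 and the target is x ≤ 5. At 5.01, 6 and 8 the target is not met, so the relaxed target works there.

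**Step 4. The bilirubin >2 x ULN row.** The enzyme part behaves as in Steps 1 and 2. The row's event is raised enzymes together with raised bilirubin, but its target is stated only as a grade, with no mention of bilirubin. If resolution includes bilirubin, the hold has length; if not, the enzyme condition is already satisfied. In both cases a restart is one level lower, or not allowed at 50 mg BID.

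**Step 5. Candidate repairs.**
- *Return to the higher of baseline and Grade 1, triggers unchanged.* Table 4 already uses baseline as a target elsewhere (retinal rows: "If resolved to baseline or Grade"; CK with renal impairment: "or baseline level. Ensure patient is adequately hydrated"). With b = 4 the target is 4. Under the both-triggers reading, x = 4.0 meets trigger and target together. A rise to x = 4.2 (0.2/4 = 5%) would be held until ≤ 4.0, then reduced after 14 days, or stopped at 50 mg BID. This does not work.
- *Split by baseline.* For b ≤ 3 the target is x ≤ 3, which no value above 3 meets at the start. For b >3 to 5 with bilirubin at most 2 x ULN, no hold applies within Grade 2 and the >5 x ULN rows govern, where x ≤ 5 is a real improvement (Step 3). This works.

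**The case against.** The strongest objection is to extent. Because Table 2 admits liver-metastasis participants up to 5 x ULN, three times baseline may be meant to replace the ULN trigger; otherwise some participants would meet the trigger at their baseline value. On that reading, baselines above 1.67 x ULN have a working target. This stands, and it narrows the point without removing it.

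A reader might infer that selumetinib restarts automatically with no recovery check. The documents do not support that. The site should consult the Sponsor during an interruption. Section 8.3.7.1 requires laboratory results to be reviewed and acceptable before each dose. Section 8.3.7 calls for repeat testing until values return to normal or baseline, or a new baseline is established. Section 6.6.1 links modification of the two drugs and favours the more conservative therapy where the tables differ, although hepatic events are not among the overlapping toxicities it lists. Table 5 withholds pembrolizumab for Grade 2 AST/ALT or bilirubin. These are real safeguards, but none states a selumetinib recovery threshold or a minimum hold.

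A reader might also infer that the bilirubin >2 x ULN row is wholly empty. That is too strong: the one-level reduction applies, and resolution could be read to include bilirubin. Nor is the DLT-based dose finding shown to be materially affected. Criterion 6 in Section 6.6.2.2 already makes related AST/ALT ≥3 x ULN with bilirubin ≥2 x ULN and alkaline phosphatase <2 x ULN a DLT, however Table 4 is read.

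**Conclusion.** The point holds in a limited form. In both Grade 2 rows, a liver-metastasis hold started at >3 to 5.0 x ULN begins with its enzyme target met, so the enzyme hold and its 14-day or 7-day test do not operate unless the value rises above 5 x ULN. The affected range is all of >3 to 5.0 x ULN if the ULN trigger applies in liver metastasis, and baselines up to about 1.67 x ULN if three times baseline replaces it. The documents do not settle which reading is meant.

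This rests on Table 4's own grade limits. In the bilirubin >2 x ULN row it is further conditional on resolution referring to enzymes alone. The number of participants affected cannot be computed from the documents, and the effect on DLT counts is small. It is still a stated safety rule that fails as written for a named subgroup, and it should be corrected.

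**What to change.** Reword Table 4 only:

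1. In both Grade 2 rows and the recurrence line, require return to Grade 1 or less for liver-metastasis participants whose baseline AST/ALT is at most 3 x ULN.
2. For liver-metastasis participants with baseline >3 to 5 x ULN, state that a value within Grade 2 with bilirubin at most 2 x ULN does not trigger a hold, and that the >5 x ULN rows govern.
3. In the bilirubin >2 x ULN row, also require bilirubin to return to 2 x ULN or less within the 7 days before restart. For participants with baseline >3 to 5 x ULN, this gives the hold its length there.

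The cost is amendment wording; baseline AST/ALT is already collected at screening. Sites must look up the baseline value, and some participants will be held longer, reduced or stopped.

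### Table 4 lets selumetinib resume after a first symptomatic Grade 4 CK elevation with renal impairment but not without it, and its two creatinine definitions overlap

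*Combined protocol and SAP*

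**What the plan says.** The CK block of Table 4 (Section 6.6.1.1) has three rows for Grade 3 and above.

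- **Grade 3 without renal impairment.** Asymptomatic: keep the dose. Otherwise: "If symptomatic (muscle pain/spasms or muscle weakness), interrupt dose of selumetinib until resolved to CTCAE Grade" 1 or below, then restart one level lower if this takes no more than 21 days, and stop if it takes longer.
- **Grade 4 (above 10 x ULN) without renal impairment.** Asymptomatic: interrupt, with the same 21-day rule. Symptomatic: a permanent stop, given in two sentences, "If symptomatic, permanently discontinue selumetinib" and "If symptomatic (muscle pain/spasms), permanently discontinue selumetinib".
- **"Grade 3 or 4 with renal impairment"**. "Interrupt selumetinib dose until resolved to Grade" below 1 or baseline; if this takes no more than 21 days, "then resume treatment at 1 reduced dose level"; stop if it takes longer or if the event recurs. The row is not divided by grade or by symptoms.

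Absence of renal impairment is defined as creatinine below 1.5 x ULN or 1.5 x baseline. Presence is defined as creatinine at or above 1.5 x ULN or 1.5 x baseline. The text before the table forbids reduction below 50 mg BID and asks the site to consult the Sponsor about stopping or restarting while a dose is interrupted.

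**The concern.** Renal impairment on top of a symptomatic Grade 4 CK rise is the worse clinical picture, yet it gets the milder first instruction. A participant with muscle symptoms and normal creatinine may never take selumetinib again. The same participant with raised creatinine may be re-exposed at a lower dose. This is a matter of participant safety, not of estimation.

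The rest of the table leads a reader to expect the opposite. In the liver rows, "Grade 3 AST or ALT" (above 5 to 8 x ULN) allows a restart when bilirubin is at most 2 x ULN, whereas AST or ALT above 5 x ULN with bilirubin above 2 x ULN is a permanent stop. There, a second abnormal signal tightens the action. The same happens within the CK block for asymptomatic Grade 3, where renal impairment changes keeping the dose into interrupting it.

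A second problem concerns which row applies. If creatinine can satisfy both definitions at once, two sites could treat the same event differently and both be following the table.

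**Working it through.** No sample-size or power figure is involved. The check sets the rows side by side and then looks for text elsewhere that overrides them.

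**Step 1. First event, by grade and symptoms.**

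| CK event | Without renal impairment | With renal impairment | Effect of renal impairment |
|---|---|---|---|
| Grade 3, asymptomatic | Keep dose | Interrupt; restart one level lower if ≤21 days | Stricter |
| Grade 3, symptomatic | Interrupt to Grade ≤1; restart one level lower if ≤21 days | Interrupt to Grade <1 or baseline; same 21-day rule; stop on recurrence | Equal or stricter |
| Grade 4, asymptomatic | Interrupt; restart one level lower if ≤21 days; no recovery grade stated | Same, with a stated target of Grade <1 or baseline; stop on recurrence | Equal or stricter |
| Grade 4, symptomatic | Permanent stop | Interrupt; restart one level lower if ≤21 days | **Milder** |

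One of the four comparisons is reversed.

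**Step 2. Who can restart.** A restart needs a lower level to go to. With a floor of 50 mg BID, a participant already at 50 mg must stop. The restart path is open to anyone whose current dose is higher, which includes all participants starting at DL2 (75 mg) or above who have not already been reduced to 50 mg.

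**Step 3. Are the two rows exclusive?** Write C for creatinine, U for ULN and B for baseline, and apply each limit to both terms.

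- Without: C < 1.5U **or** C < 1.5B, that is, C < 1.5 × max(U, B).
- With: C ≥ 1.5U **or** C ≥ 1.5B, that is, C ≥ 1.5 × min(U, B).
- Both hold when 1.5 × min(U, B) ≤ C < 1.5 × max(U, B). This range is empty only if U = B.

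An illustration with assumed values: U = 1.2, B = 0.7, C = 1.2. Then 1.5U = 1.8 and 1.5B = 1.05. Creatinine is below 1.8, so the first definition is met, and at or above 1.05, so the second is met too. For these values any creatinine from 1.05 to just under 1.8 fits both rows. The reverse case (B above U) can also arise, because Table 2 admits participants with creatinine above ULN. In the overlap, a symptomatic Grade 4 event carries both a permanent stop and an interrupt-and-restart instruction.

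**Step 4. Does other text settle it?**

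- Section 6.6.1 says that, where the tables propose two therapies, "the most conservative/effective treatment should be chosen", and gives steroid as its example. It concerns treatment of the event. It might be stretched to dose action when both CK rows apply, but it does not clearly do so. When creatinine falls in only one row there is nothing to choose between.
- The Grade 4 stop for all other adverse events does not reach CK elevation, which has its own rows. It could apply if the event were recorded under a different diagnosis (Section 10.3.4), but that depends on coding and grading.
- Table 5 on renal dysfunction and other immune-related events sets pembrolizumab actions and depends on attribution. It sets no selumetinib rule for a CK event.
- Sponsor consultation (Section 6.6.1.1), the unnecessary-risk criterion (Section 7.1) and laboratory review before dosing (Section 8.3.7.1) all rest on judgment.

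None of these expressly removes the reversal.

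**The case against.** The best defence is that the documents do not show the renal row to be too lenient; the non-renal row may simply be strict. Table 4 is a guideline with recommendations, and nothing states what was intended. Restarting after a Grade 4 event is not foreign to it: Grade 3 to 4 diarrhea also allows a restart one level lower, with no time limit in that row. The renal row has its own safeguards: recovery below Grade 1 or to baseline, the 21-day limit, a reduced dose, and a stop on recurrence. Sponsor consultation and laboratory review stand behind them.

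Much of this is right. It limits the point to one case and rules out calling the row a proven error. It does not explain why a mandatory stop should become a discretionary one when renal impairment is added, and the documents offer no reason.

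Three stronger readings are tempting and are not supported.

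- *The two rows exclude each other on creatinine, so every participant falls in exactly one.* Step 3 shows that they do not. For participants in the overlap the finding is conflicting instructions, not a clean reversal.
- *Muscle weakness is left out at Grade 4.* The unrestricted sentence, "If symptomatic, permanently discontinue selumetinib", already covers it, so the duplication is editorial.
- *The reversal distorts the DLT count or the mTPI decisions.* A treatment-related stop in Cycle 1 meets DLT criterion 8 in Section 6.6.2.2. A renal case that is only interrupted would need another criterion, such as 4 (laboratory abnormality with intervention, hospitalization or persistence beyond a week) or 9 (more than 25% of selumetinib doses missed), and may often meet one. The documents do not establish a distortion, and the mTPI rules do not change.

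**Conclusion.** The point holds in a narrow form. For a first symptomatic Grade 4 CK elevation in a participant above 50 mg BID, added renal impairment gives the milder instruction: a possible restart one level lower instead of a permanent stop. The other three comparisons are equal or stricter with renal impairment. Separately, the creatinine definitions overlap whenever ULN and baseline differ, so some participants literally fit both rows.

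One in four is a count of table cells, not a measure of risk. The documents give no frequency for this event, and CK is measured only as clinically indicated (Section 1.3), so no number of affected participants can be given. The conclusion rests on reading the rows as printed and on applying 1.5 x to both ULN and baseline. Whether the difference was intended is unknown. The direction of the fix follows the table's own pattern in the liver rows and in asymptomatic Grade 3 CK. It is a change the sponsor should make, or else state the reason for the difference.

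**What to change.** 1. **Split the renal row.** Grade 4 with renal impairment, symptomatic (muscle pain, spasms or weakness): permanent selumetinib stop. Grade 3 with renal impairment, and asymptomatic Grade 4 with renal impairment: keep the present text, including the recovery target, the 21-day limit and the stop on recurrence.
2. **Make the definitions exclusive.** Without renal impairment: creatinine below 1.5 x ULN **and** below 1.5 x baseline. With renal impairment: creatinine at or above 1.5 x ULN **or** at or above 1.5 x baseline.

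The two belong together. The second change alone would place everyone in the overlap in the renal row, which is now the milder one for symptomatic Grade 4.

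Merging the two symptomatic sentences in the Grade 4 row into one that uses the Grade 3 symptom definition is optional tidying.

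The cost is a protocol amendment to one block of Table 4, with no effect on analysis or sample size. The downside is that a few participants who might have resumed at a lower dose will stop, and that asymptomatic Grade 3 events in the overlap will clearly require interruption where the present text also allows the dose to be kept.
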